12.4. Clinical Laboratory Evaluation

Shift tables (i.e., normal, abnormal not-clinically significant, abnormal clinically significant at baseline versus normal, abnormal not-clinically significant, abnormal clinically significant at follow-up in a 3-by-3 contingency table) will be provided to assess changes in laboratory values from baseline to follow-up result. The counts and percentage of subjects with each of the 9 possible “shift” outcomes will be calculated by treatment arm.

12.5. Pharmacokinetics and Skin Biopsy

HGF serum level and copies of VM202 will be summarized by treatment arm at each visit using descriptive statistics for continuous variables. This will be performed by independent lab. An independent analyses report on the histological findings on skin biopsy will be provided by an independent lab as well.

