SCHEDULE OF EXAMINATIONS	Screening (Day -60 to Day 0) Day 0 Day 14 ± 1 days Day 21 ± 3 days Day 30 ± 3 days Day 60 ± 3 days Day 90 ± 7 days Month 6 ± 1 month Month 9 ± 1 month
STUDY ENDPOINTS	The primary study endpoint is the change in the average 24 hour pain score (change from baseline to the 6-month follow-up). The difference in the mean of the change in the average 24-hour pain score will be compared between the treatment groups and the placebo arm to determine the treatment effect. The average pain scores will be obtained from the Daily Pain and Sleep Interference Diary (recorded daily by the patient for 7 days during Screening prior to the first round of injections and again, before the 6 month follow-up).
SAFETY	Any subject who receives study drug (VM202 or placebo) will be included in the safety analysis population. Adverse events (including serious adverse events, and adverse events leading to treatment discontinuation) throughout the 9 months follow-up will be described according to severity and to their relationship with the study drug and injection procedure. Descriptive statistics (N, mean, median, SD, minimum and maximum values, where applicable) will be used to characterize safety parameters.
	All subjects will undergo testing as presented in the American Cancer Society Cancer Screening Guidelines as part of their baseline testing to rule out cancer.
PHARMACOKINETICS	Determination of HGF serum levels will be determined immediately pre-treatment on Day 0, immediately pre-treatment on Day 14, on Day 30, Day 60, and Day 90. The number of copies of VM202 in whole blood will be determined at Day 0 (pre-injection, and 2 hours [± 1 hour] post injection), at Day 14 (pre-injection, and 2 hours [± 1 hour] post injection), Day 21, Day 30, Day 60 and Day 90.
OTHER EFFICACY MEASURES	The 24 hour average pain score obtained from the Daily Pain and Sleep Interference Diary will be compared at all other study visits,

as will the Brief Pain Inventory for Diabetic Peripheral Neuropathy (BPI-DPN), the VAS score obtained during follow-up visits, symptoms of the Brief Peripheral Neuropathy Screening (BPNS), the Patients' Global Impression of Change (PGIC), MNSI, and histological findings on skin biopsy.

TABLE OF CONTENTS

INVESTIGATOR'S AGREEMENT.....	2
STUDY SYNOPSIS	3
TABLE OF CONTENTS	10
ABBREVIATIONS	14
PERSONNEL AND FACILITIES.....	15
1. BACKGROUND.....	16
1.1. Diabetes	16
1.1.1. Diabetic Peripheral Neuropathy	16

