1.3. HGF FOR THE TREATMENT OF DIABETIC NEUROPATHY

Hepatocyte growth factor (HGF) has been shown to be a potent angiogenic growth factor, stimulating the growth of endothelial cells and migration of vascular smooth muscle cells.^{24,25} It is a multi-functional mesenchyme-derived cytokine with potent angiogenic and anti-apoptotic effects.²⁴⁻²⁷ HGF stimulates DNA, RNA and protein synthesis by endothelial cells in a dose-dependent manner and attenuates high D-glucose-induced endothelial cell death. HGF has also been shown to upregulate vascular endothelial growth factor (VEGF) expression, and has demonstrated greater mitogenic activity than that of VEGF alone in human aortic endothelial cells *in vitro*.^{28,29} Recently, HGF gene transfer has been shown to produce significant augmentation of collateral formation in the rabbit hind limb ischemia model.²⁵ Furthermore, a significant increase in blood flow was achieved by HGF gene transfer both in rat diabetic and non-diabetic hind limb ischemia models.^{27,30}

Recent research also indicates that HGF can function as a neurotrophic factor.³¹ Sympathetic neurons co-express bioactive HGF, its cognate receptor (the Met receptor), and localized exogenous HGF has been shown to promote the growth (but not survival) of sympathetic neurons.³²⁻³⁶ It is proposed that administration of HGF may promote axonal growth and regeneration. As loss of microvasculature in diabetic neuropathy has also been implicated in acceleration of neuronal loss and pain symptoms,³⁷ HGF may be an ideally suited candidate for the treatment this condition. Exogenous VEGF has been studied in this patient population, but with limited success.³⁸⁻⁴¹

The challenge associated with delivering a targeted sustained dose of exogenous HGF is in overcoming the instability of HGF in blood circulation and its rapid clearance by the liver; HGF has an *in vivo* half-life of less than 15 minutes.^{42,43}

[figure not shown]
One approach to increasing HGF in ischemic tissues is to develop a gene transfer strategy that would allow for persistent expression of HGF protein *in vivo*. Although plasmid DNA is one of the least efficient gene transfer systems currently in use, the fact that it is associated with limited persistence and no propensity for genomic integration, (particularly in skeletal muscle tissue) makes it an attractive option for local targeted delivery.

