1.6.3. PHASE I/II STUDY IN PATIENTS WITH PAINFUL DPN

VM202 was evaluated for treatment of DPN in an ongoing prospective, dose-escalation Phase I study. The study consisted of three (3) cohorts of four (4) subjects. Subjects received 4 mg, 8 mg, or 16 mg VM202 unilaterally in a calf. For each dose cohort, VM202 was administered as local intramuscular injections with half of the dose administered at Day 0 of the study and the second half administered

2 weeks later. Preliminary efficacy (hemodynamic assessments), safety and tolerability were evaluated at Baseline (screening) and at designated time points throughout the study. All 3 dose cohorts were followed for one year from the time of the first dose of study drug administration. Between June 2010 and March 2011, twelve (12) subjects were enrolled in the study, and enrollment and follow-up are complete.

Ten out of 12 subjects (10/12, 83%) experienced a reduction in pain at their 6 month visit. One patient each in Cohort I and Cohort II did not experience a reduction in pain. At 6 month, mean change in VAS was -8.2 in Cohort I, -31.6 in Cohort II and -25 in Cohort III.

At 12 month, 9 out of 12 subjects (9/12, 75%) experienced a reduction in pain. The same 2 patients, one each in Cohort I and Cohort II did not experience a reduction in pain, and one patient in Cohort III returned to baseline levels at 12 month. At 12 month, mean change in VAS was -12.0 in Cohort I, -32.8 in Cohort II and -18.5 in Cohort III. VAS scores also tracked well with other quality of life measures (BPI-DPN).

Intramuscular injections of VM202 appear to be well tolerated at doses as high as 16 mg in patients with DPN. There were no incidents of dose limiting toxicities (DLT). There have been no serious or unexpected adverse events in the study. The level of VM202 DNA was below the LLOQ in all 12 subjects by day 90. Circulating HGF levels remained relatively constant throughout the study, suggesting that the plasmid remained active only at the injection site.

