3.4.10. DAY 21 \pm 3 DAYS

- Concomitant Medications
- Vital Signs
- Copies of VM202 in whole blood
- Injection site assessment
- Adverse event assessment

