6.3.4. PHARMACODYNAMICS

HGF serum levels will be determined immediately pre-treatment on Day 0, immediately pre-treatment on Day 14, on Day 30, Day 60, and Day 90. Copies of VM202 in whole blood will be determined at Day 0 (pre-injection and 2 hours post injection), at Day 14 (pre-injection and 2 hours post injection), Day 21, Day 30, Day 60 and Day 90.

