Appendix 5. Test Article Administration

1. *Test article preparation*

VM202 - VM202 is supplied in a sterile glass vial containing 2.5 mg of lyophilized study product. Before administration, it will be reconstituted with 5.0 mL of water for injection (WFI) for a final VM202 concentration of 0.5 mg / mL. Each reconstituted vial is only to be used for one subject. For subjects randomized to the Low Dose or High Dose arms of the study, the final doses of VM202 will be divided evenly between the Day 0 administration and the Day 14 administration. Every individual injection will be 0.5 mL. All injections administered by intramuscular injections.

Placebo - Patients assigned to either the placebo arm or the Low Dose arm will receive normal saline injections. The placebo group will receive only normal saline injections; the Low Dose arm will receive 16 injections of VM202 and 16 injections of normal saline in each leg at both injection visits. Visually, normal saline is indistinguishable from reconstituted VM202.

Table 4. Single dose preparation and delivery for Day 0 and Day 14 Visits

Treatment Arm	Number of Vials Reconstituted at each visit	Number of injections [†] / leg	Total Volume to be Injected / leg
Low Dose 8 mg/ leg Total Dose:16 mg VM202	4 Vials VM202, reconstituted with WFI	16 of VM202 16 of placebo	16 mL
High Dose 16 mg/ leg Total Dose:32 mg VM202	8 Vials VM202, reconstituted with WFI	32 of VM202	16 mL
Placebo – Normal Saline	NA – Normal Saline	32 of placebo	16 mL

[†]Injection volume for each individual injection = 0.5 mL

2. **Test material administration** – Patients will receive injections of VM202 or placebo on Day 0, and Day 14. A fine needle (e.g. 27 gauge, 1") suitable for IM injections will be used. **Both calves will be treated with 32 injections each at each visit.** Distribute injection sites evenly over the calf muscle, carefully avoiding fascia.
3. Inject the entire amount of the drug per each injection in about 3-5 seconds. Immediately after completion of injection, lightly press the injection site with the finger head in order to prevent reflux. Do not massage the injection site. An indelible marker should be used to identify each injection site.

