12.6. Vital Signs

Vital signs and change from baseline will be summarized descriptively at each visit by treatment arm.

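### No scheduled serum HGF sample falls less than 12 days after the preceding injection, and SAP 12.5 reports raw levels only: a short-lived rise would be missed and a sustained one measured less precisely than the data allow

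*SAP*

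**What the plan says.** **Sampling.** Protocol 6.3.4 fixes the times: "HGF serum levels will be determined immediately pre-treatment on Day 0, immediately pre-treatment on Day 14, on Day 30, Day 60, and Day 90". Protocol 4.2.5, the laboratory schedule in Protocol Appendix 1 and SAP Table 2 agree that the Day 0 and Day 14 samples precede the injection. Protocol Appendix 5 gives the dosing days: "Patients will receive injections of VM202 or placebo on Day 0, and Day 14". The synopsis gives the windows: "Day 0 Day 14 ± 1 days Day 21 ± 3 days Day 30 ± 3 days".

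The plasmid is followed more closely than the protein it expresses. The Day 21 visit (Protocol 3.4.10) lists "Copies of VM202 in whole blood" but no serum HGF. Protocol 4.2.6 also takes blood for copies 1 to 3 hours after each injection. Protocol 3.5.2 adds one unscheduled HGF sample for a subject who withdraws before Day 90.

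**Analysis.** SAP 12.5 states that "HGF serum level and copies of VM202 will be summarized by treatment arm at each visit using descriptive statistics for continuous variables", and that an independent laboratory does this work. The next section, SAP 12.6, does use the baseline: "Vital signs and change from baseline will be summarized descriptively at each visit by treatment arm". SAP 9 defines baseline as the last value on or before the start of dosing, which for HGF is the Day 0 pre-dose sample.

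**Background.** Protocol 1.3 notes that "HGF has an *in vivo* half-life of less than 15 minutes". Of the earlier study in this disease, Protocol 1.6.3 says: "Circulating HGF levels remained relatively constant throughout the study, suggesting that the plasmid remained active only at the injection site".

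**The concern.** With a half-life of minutes, a serum value reflects HGF released at about the time of the draw. It carries no memory of what happened a week before. If release into the circulation peaks in the days after injection and then fades, none of the scheduled samples is placed to see it.

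Safety is the primary objective (SAP 2.1), and serum HGF is the only planned measure of the expressed protein in the circulation. The protocol describes HGF as strongly angiogenic, excludes recent malignancy and proliferative retinopathy, and repeats fundoscopy at 9 months, so systemic exposure bears on safety. The inference at risk is one that the protocol has already drawn, from steady HGF to activity at the injection site alone. The earlier study does not settle the matter here. It gave at most 16 mg, in one calf, against up to 32 mg over both calves in this trial, and the protocol does not say when its HGF samples were taken.

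HGF is also an endogenous protein with its own spread between people. A summary that leaves each subject's pre-dose value unused carries that spread into every comparison with placebo.

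**Working it through.** The documents give no power or precision figure for HGF, so there is none to reproduce.

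**1. Gap from the latest injection to each draw.** Dose 1 is on Day 0. Dose 2 is on Day 14 ± 1, so between Days 13 and 15. The shortest gap is the earliest visit day minus 15; the longest is the latest visit day minus 13.

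| Draw | Arithmetic | Gap (days) |
|---|---|---|
| Day 14 pre-dose | 13 to 15, from dose 1 | 13 to 15 |
| Day 30 ± 3 | 27 − 15; 33 − 13, from dose 2 | 12 to 20 (nominal 16) |
| Day 60 ± 3 | 57 − 15; 63 − 13 | 42 to 50 |
| Day 90 ± 7 | 83 − 15; 97 − 13 | 68 to 84 |
| Day 21 ± 3 (copies only, no HGF) | 18 − 15; 24 − 13 | 3 to 11 (nominal 7) |

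The shortest scheduled HGF gap is 12 days. Adding HGF at Day 21 would make it 3.

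**2. Precision of one dose arm against placebo.** Arm sizes are 40 and 20 (SAP 4). The documents give neither the SD of HGF nor the correlation r between pre-dose and follow-up values. Results are therefore in SD units over an assumed range of r, with the same SD at both times.

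- Raw level: t(0.975, 58 df) × √(1/40 + 1/20) = 2.002 × 0.2739 = 0.548 SD.
- Change from Day 0: multiply by √(2(1 − r)).
- Adjusted for Day 0 (ANCOVA): multiply by √(1 − r²), ignoring the one degree of freedom spent on the covariate.

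| Assumed r | Raw | Change | Adjusted |
|---|---|---|---|
| 0.3 | 0.548 | 0.649 | 0.523 |
| 0.5 | 0.548 | 0.548 | 0.475 |
| 0.7 | 0.548 | 0.425 | 0.391 |
| 0.9 | 0.548 | 0.245 | 0.239 |

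Adjustment narrows the interval by 13% at r = 0.5 and 29% at r = 0.7. Subtraction alone helps only when r exceeds 0.5, and loses precision below that. On raw levels, the difference detectable with 80% power at two-sided 0.05 is (1.960 + 0.842) × 0.2739 = 0.77 SD.

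**3. What Day 21 would add.** Suppose expression is highest at injection and falls with half-life T. Both are assumptions; the documents give neither. The share of the initial signal left at t days is 2^(−t/T), with t = 7 for nominal Day 21 and t = 16 for nominal Day 30.

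| Assumed T (days) | Day 21 | Day 30 | Ratio |
|---|---|---|---|
| 3 | 20% | 2% | 8 |
| 5 | 38% | 11% | 3.5 |
| 10 | 62% | 33% | 1.9 |
| 20 | 78% | 57% | 1.4 |

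The gain is large if expression is brief and small if it persists.

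**The case against.** A reader might infer that the trial can neither show nor rule out any systemic rise in HGF. The documents do not support that. Levels are summarised by arm before dosing and at Days 14, 30, 60 and 90, with a concurrent randomised placebo arm. A rise lasting about two weeks or more would show, with a half-width of about 0.55 SD even on raw levels. With complete data the mean change equals the difference between the two visit means, so leaving out the subtraction costs precision and the SD of the change, not the ability to see a shift.

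Nor is it right that HGF is never sampled within 12 days of an injection. The Day 0 and Day 14 samples are taken immediately before one, a 12-day gap is itself allowed, and an early-withdrawal or out-of-window sample could come sooner. Such samples are sporadic, though, and do not amount to planned coverage of the early period.

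Day 21 is not the draw closest to a dose: blood for copies is already taken 1 to 3 hours after each injection. A single Day 21 sample would, by the same half-life argument, speak only for that day. Protocol 1.3 also describes the aim of gene transfer as persistent expression, in which case Day 30 would lose little.

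The title of SAP Table 16 proves nothing by itself. The vital-signs table title omits change too, although SAP 12.6 requires it. The independent laboratory may have its own plan, which is not among the documents. HGF carries no formal hypothesis; adverse events, laboratory shifts, vital signs and fundoscopy bear most of the safety objective. The SAP does not itself plan to conclude local action from flat means.

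All of this narrows the point. What stands is that no scheduled sample covers roughly the first 12 days after either dose, and that SAP 12.5 makes no stated use of a baseline already collected.

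**Conclusion.** The point holds for transient rises and for precision, and no further. The 12-day minimum gap follows from the protocol's own windows and needs no assumption. That a rise confined to this period would go unseen follows from the gap together with the protocol's stated half-life. The loss of precision depends on a correlation that the documents do not give: moderate at 0.5 to 0.7, slight at 0.3. The benefit of a Day 21 sample depends on an expression time course that they do not give either.

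This is an inexpensive improvement to a descriptive safety measure. It does not call the primary efficacy analysis or the main safety summaries into question.

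**What to change.** 1. **SAP 12.5.** For each post-dose visit, add the difference of each dose arm from placebo in serum HGF, adjusted for the Day 0 pre-dose value by ANCOVA, with a 95% CI. Show descriptive change from Day 0 beside it; change alone is not a substitute, because it gains precision only when the correlation exceeds 0.5. Carry the same specification into the independent laboratory's analysis plan. Cost: wording and programming; the data are already collected.

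2. **Protocol 3.4.10, 4.2.5 and Appendix 1, with SAP Table 2 and the other listings of HGF times brought into line.** Add a serum HGF tube to the Day 21 draw already made for VM202 copies. Cost: one further 6 cc tube per subject and about 100 assays (100 subjects × 1 visit), with no new visit or needle stick.

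3. **Study report.** Even with Day 21 added, at least the first 3 days after dose 2 and the 13 days after dose 1 have no scheduled sample. State this, and limit any conclusion that the product acts only locally to the times actually sampled. Cost: wording only.

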12.6. Vital Signs

Vital signs and change from baseline will be summarized descriptively at each visit by treatment arm.

12.7. Retinal Fundoscopy

A retinal fundoscopy of each eye will be performed at Screening and at 9 Months (or last available visit for early withdraw). Each eye will be given one of the following assignments: Normal, Abnormal-Not Clinically Significant, and Abnormal-Clinically Significant. Shift tables will be provided to assess changes in retinal fundoscopy. For each of the three treatment groups, counts and percentage of subjects will be calculated for each of the 9 possible “shift” outcomes.

12.8. Prior and Concomitant Medications

Prior medications are those medications taken within 60 days prior to the initial dose of study drug. Concomitant medications are those medications taken after the initial dose of study drug. Prior and concomitant medications will be summarized for each treatment by medication name. These summaries will present the number and percentage of subjects using each medication.

12.9. Interim Analyses

An independent data safety monitoring board (DSMB) will review a limited set of un-blinded tables and listings, including all reported SAEs. There will be no adjustment for multiple testing because the results of the interim analysis will not be used to declare the study a success, the unblinded analyses will be performed by a person independent to the study project statistician, and the detailed unblinded findings will not be shared with the project team.

APPENDIX A: LIST OF TABLES

Table Number	Table Description
1	Subject Disposition And Accountability
2	Demographic Characteristics (Efficacy Analysis Group/ITT Group/Safety Analysis Group)
3	Abnormal Medical History at Baseline (Safety Analysis Group)
4	Peripheral Vascular Disease Intervention History (Safety Analysis Group)
5.1	Visual Analogue Scale for 24-hour Average Pain from Daily Pain and Sleep Interference Diary (Efficacy Analysis Group)
5.2	Visual Analogue Scale for 24-hour Average Pain from Daily Pain and Sleep Interference Diary (ITT Group)
5.3	Visual Analogue Scale for 24-hour Average Pain from Daily Pain and Sleep Interference Diary (ITT Group with Missing Value Imputation at 6 Months)
6.1	Visual Analogue Scale for Pain (Efficacy Analysis Group)
6.2	Visual Analogue Scale for Pain (ITT Group)
7.1	Brief Pain Inventory for Diabetic Peripheral Neuropathy (BPI-DPN) (Efficacy Analysis Group)
7.2	Brief Pain Inventory for Diabetic Peripheral Neuropathy (BPI-DPN) (ITT Group)
8.1	Michigan Neuropathy Screening Instrument (MNSI) (Efficacy Analysis Group)
8.2	Michigan Neuropathy Screening Instrument (MNSI) (ITT Group)
9.1	Patients' Global Impression of Change (PGIC) (Efficacy Analysis Group)
9.2	Patients' Global Impression of Change (PGIC) (ITT Group)
10.1	24-hour Average Pain Interference with Sleep from Daily Pain and Sleep Interference Diary (Efficacy Analysis Group)
10.2	24-hour Average Pain Interference with Sleep from Daily Pain and Sleep Interference Diary (ITT Group)
11	Study Drug Exposure(Safety Analysis Group)
12	Injection Site Reaction (Safety Analysis Group)
13.1	Adverse Events by Preferred Term (Safety Analysis Group)
13.2	Adverse Events by Maximum Severity (Safety Analysis Group)
13.3	Adverse Events by Relationship to Study Drug (Safety Analysis Group)
13.4	Serious Adverse Events by Preferred Term (Safety Analysis Group)
13.5	Serious Adverse Events by Maximum Severity (Safety Analysis Group)
13.6	Serious Adverse Events by Relationship to Study Drug (Safety Analysis Group)
14.#	Hematology – Test # Shift from Baseline (Safety Analysis Group)
15.#	Chemistry – Test # Shift from Baseline (Safety Analysis Group)
16	HGF Serum Level (Safety Analysis Group)
17.#	Vital Signs – Parameter # (Safety Analysis Group)

18	Retinal Fundoscopy- Shift from Baseline (Safety Analysis Group)
19	Prior and Concomitant Medications (Safety Analysis Group)
